## LIST OF ABBREVIATIONS

AE	adverse event
CBC	complete blood count
CNS	central nervous system
CR	complete response
CRF	case report form
CTCAE	Common Terminology Criteria for Adverse Events
CTLA-4	cytotoxic T lymphocyte-associated protein 4
DSMC	Data and Safety Monitoring Committee
eCRF	electronic case report form
FDA	Food and Drug Administration
GTV	gross tumor volume
Gy	gray
IIT	investigator-initiated trial
irAE	immune-related adverse event
iRANO	immunotherapy Response Assessment in Neuro-Oncology
irRC	immune-related response criteria
IRB	Institutional Review Board
ITV	Internal tumor volume
MCC	Massey Cancer Center
NCI	National Cancer Institute
PD-1	programmed death receptor-1
PD-L1	programmed death-ligand 1
PR	partial response
PRMC	Protocol Review and Monitoring Committee
PTV	planning target volume
RANO-BM	Response Assessment in Neuro-Oncology for Brain Metastases
RECIST	Response Evaluation Criteria in Solid Tumors
RT	radiation therapy
SAE	serious adverse event
SBRT	stereotactic body radiotherapy
SD	stable disease
SRS	stereotactic radiosurgery
SRT	stereotactic radiotherapy
TRegs	regulatory T cells
UP	unanticipated problem
VCU	Virginia Commonwealth University
WCBP	woman of childbearing potential

## STUDY SCHEMA

# 1 BACKGROUND

## 1.1 Radiotherapy and the Abscopal Effect

The immune system distinguishes “self” from “non-self,” and targets “non-self” for elimination. This process forms the basis of our immunity to pathogens and the primary barrier to organ transplantation. Cancer, however, is neither “self” nor “non-self,” but rather “altered-self” and evades detection and elimination by the immune system through multiple mechanisms. The ultimate goal of cancer immunotherapy is to target and reverse these tumor-induced immunosuppressive processes, allowing the activated immune system to eradicate the cancer and develop immunologic memory to combat future recurrences before they become clinically apparent ([1](#)).

Radiotherapy has been a primary oncologic therapeutic modality for approximately a century, and it was recognized prior to 1950 that in rare circumstances, radiation of a single tumor resulted in regression of not only the irradiated tumor, but also regression of distant tumors not irradiated. This phenomenon was termed “The Abscopal Effect.” Contemporary preclinical work from various tumor immunology groups have demonstrated that the abscopal effect is mediated by the immune system ([2](#), [3](#)).

## 1.2 Biologic Rationale for Combining Immunotherapy and Stereotactic Radiotherapy

Stereotactic radiotherapy (SRT), in which large radiation doses per fraction are given, has been combined with immunotherapy to potentiate the abscopal effect of radiotherapy ([1](#)). A recent review describes the biologic rationale for combining immunotherapy and SRT. Tumor cells can downregulate major histocompatibility complex I (MHC I) expression to avoid immune system detection ([4](#)). One possible mechanism of the abscopal effect of radiation is upregulation of MHC I expression after radiation, which eliminates tumor cells’ ability to evade immune detection via this pathway ([3](#), [5](#), [6](#)). Radiation also increases the quantity of tumor-specific antigens for immune presentation ([7](#)). However, upregulation of MHC I expression and increased antigen supply are insufficient – activated T cells must be present to recognize and kill the tumor cells ([1](#), [6](#)).

Both cytotoxic T lymphocyte-associated protein 4 (CTLA-4) inhibitors, by keeping T cells activated for longer periods, and programmed death receptor-1 (PD-1) or programmed death-ligand 1 (PD-L1) inhibitors, by preventing apoptosis of T cells, can potentiate the abscopal effect of radiotherapy. However, a documented mechanism of tumor resistance to CTLA-4 inhibition is upregulation of PD-1 activity ([8](#)). Preclinical work has shown that PD-1 activity can moderate the abscopal effect of radiation therapy ([9](#), [10](#)), and that tumors can increase PD-1 activity after radiotherapy ([11](#)). Correspondingly, a documented mechanism of tumor resistance to PD-1 inhibition is downregulation of MHC I expression ([1](#)). Therefore, the combination of SRT and PD-1 inhibiting therapy may offer enhanced tumor responses by disrupting known resistance mechanism to both individual therapies.

In murine models, the combination of immune checkpoint inhibitors and SRT generated more robust treatment responses than either individually ([9](#), [11-15](#)). In murine melanoma and mammary carcinoma models, SRT augmented the response of combined PD-1 and CTLA-4 inhibition, even in cell lines previously resistant to CTLA-4 inhibition ([8](#)).

### 1.3 Clinical Experience with Immunotherapy and Stereotactic Radiotherapy

Within the past 5 years, immune checkpoint inhibitors such as nivolumab and pembrolizumab (PD-1 inhibitors), atezolizumab and durvalumab (PD-L1 inhibitors), and ipilimumab (a CTLA-4 inhibitor) have demonstrated improved outcomes in patients with advanced solid tumors, first in melanoma ([16-21](#)) and subsequently in non-small cell lung cancer (NSCLC), renal cell carcinoma (RCC), squamous cell carcinoma of head and neck (SCCHN), and bladder cancer ([22-36](#)), among others, leading to approval by the US Food and Drug Administration (FDA) for their use in these cancers with additional indications expected in the near future.

Despite these dramatic improvements in patient outcomes, the majority of cancers progress on PD-1 and PD-L1 inhibitors, leaving them few options for treatment. While conventional thinking suggests that there is no further role for re-use of cytotoxic therapy or targeted therapy once tumors are resistant to those agents, immune checkpoint inhibitors may be different. As these agents do not target the tumor directly, the immune system may be more dynamic, and there may be modulations that can allow immune checkpoint inhibition to gain tumor control following initial progression while on these agents. Formal exploration of re-treatment strategies could begin to shed light on this process, and open new opportunities for therapy.

Multiple groups have published case reports of patients who were failing immune checkpoint immunotherapy until they received SRT to a single lesion, after which regression of the irradiated lesion as well as lesions outside of the radiation field with attendant changes in molecular markers of immune activation was observed ([1](#), [37](#), [38](#)). Similarly, radiotherapy to oligo-progressive metastatic lesions has been shown to prolong the efficacy of tyrosine kinase inhibitors in lung cancer ([39](#), [40](#)). These reports have fueled a growing area of clinical investigation into the combination of radiotherapy and immunotherapy.

### 1.4 Rationale for PD-1 and PD-L1 Inhibitors Versus CTLA-4 Inhibitors

The efficacy of PD-1 inhibition versus CTLA-4 inhibition has rarely been directly evaluated. PD-1 inhibitors have been shown to be effective in patients with melanoma that has previously progressed on ipilimumab ([41-43](#)). In a three-arm phase 3 trial comparing ipilimumab (a CTLA-4 inhibitor), nivolumab (a PD-1 inhibitor), and dual immune therapy in treatment-naïve patients with unresectable or metastatic melanoma, nivolumab demonstrated superior response rates and progression-free survival compared to ipilimumab ([44](#)). These results were replicated with pembrolizumab compared to ipilimumab ([45](#)).

PD-1/PD-L1 inhibition and CTLA-4 inhibition target distinct pathways and have different mechanisms of action ([46](#)). Since PD-1 pathway inhibition has demonstrated superior response to CTLA-4 inhibition in melanoma ([18](#), [44](#)) and has proven effective in multiple cancer histologies after progression on CTLA-4 inhibition ([8](#), [41-43](#)), we have decided to pursue the combination of PD-1 or PD-L1 inhibiting therapy and SRT rather than CTLA-4 inhibiting therapy and SRT. The toxicity profile of PD-1 inhibition appears to be more favorable than that of CTLA-4 inhibition ([44](#)). Should our initial study demonstrate favorable outcomes, then the combination of SRT and dual immune therapy could be evaluated in a subsequent study, given the excellent responses of dual immune therapy seen in melanoma.

Although both classes of immune therapy have approval in melanoma, PD-1 inhibitors have FDA approval for use in NSCLC, RCC, and SCCHN, with additional indications expected in the near future. Also, the PD-L1 inhibitor, atezolizumab, has been approved by the FDA for

treatment of metastatic urothelial carcinoma, with additional indications expected in the near future. Therefore, the use of PD-1 and PD-L1 inhibitors, instead of CTLA-4 inhibitors, expands the eligible population now in this study and in the future.

## **1.5 Inclusion of Multiple Advanced Solid Tumors**

PD-1/PD-L1 inhibiting therapy has demonstrated efficacy in multiple tumor types. Similarly, the abscopal effect has been seen in multiple tumor types ([47-57](#)). By limiting our population to patients who have demonstrated disease control on PD-1 or PD-L1 inhibiting therapy, we select patients with tumors that have the highest likelihood of responding to further immune modulation with radiotherapy and continued immunotherapy. This population is also consistent with the patients described in case reports of combining SRT and immunotherapy. Our plans for statistical methodology that includes both overall and disease-specific futility assessments increases the likelihood of identifying tumor types that respond to combination therapy.

## **1.6 Inclusion of Brain Metastases**

While patients with brain metastases were excluded from most of the seminal studies leading to the adoption of PD-1 and PD-L1 inhibiting therapy, PD-1 inhibitors have demonstrated efficacy in brain metastases ([58, 59](#)), and the combination of SRT and PD-1 inhibitors in the treatment of brain metastases has been shown to be safe ([60, 61](#)). Additionally, the reduced blood brain barrier seen in brain metastases suggests that radiotherapy to these lesions offers a similar, if not identical, chance for immune reactivation compared to radiotherapy to extracranial sites ([62](#)).

Our radiation oncology group is not comfortable with observing intracranial disease given the potential for these lesions to quickly cause debility and/or death. Therefore, patients with brain metastases will be included in this study provided all brain lesions can be treated with SRT and there is extracranial measurable disease that can be observed. Given the limited data on the immunogenicity of brain metastases, enrollment of patients who receive SRT to brain metastases alone will be limited and their data analyzed separately.

## **1.7 Opportunity for Novel Investigation**

Most of the recent clinical trials evaluating the combination of SRT and immunotherapy are enrolling patients who are naïve to immunotherapy, and recently published studies in melanoma, prostate cancer, and other solid malignancies investigated immunotherapy-naïve patients ([8, 63-65](#)). However, in the seminal case report detailing the abscopal effect in a patient with metastatic melanoma, the patient, who had previously responded to ipilimumab but was progressing on immunotherapy, received SRT to a painful paraspinal metastasis while continuing immunotherapy ([37](#)).

To date, no studies have prospectively examined combination therapy in patients with tumors that have progressed on prior immune checkpoint inhibiting therapy, recreating the conditions described in prior case reports. In this clinical trial, SRT and immunotherapy will be combined to treat patients who have had disease control from immunotherapy but did not continue to improve.

## 1.8 Volumetric Measurements for Response Assessment

Most criteria for evaluating treatment response use unidirectional or 2-dimensional tumor measurements to assess response. In this study, the feasibility of using volumetric measurements of tumor size will be explored.

## 1.9 Evaluation of Immunologic Correlates Using Blood Samples

### 1.9.1 Significance and Background

The mechanisms underlying radiation therapy (RT)-induced antitumor immune responses are complex, but are likely related to secretion of certain immunostimulatory cytokines and chemokines, systemic immune response against tumor antigens, systemic signaling by exosomes released from tumor cells, and local inflammation contributing to a distant effect ([66](#)). For example, serum IFN- $\gamma$  levels were found to increase in a dose-dependent fashion in patients with esophageal squamous cell carcinoma who were treated with RT alone. Type I interferons (IFN- $\alpha$  and IFN- $\beta$ ) not only play important roles in the immune responses to viral infection, but are also actively involved in antitumor immunity ([67](#)). RT can induce production of Type I interferons through activation of intracellular DNA sensors, such as the STING-dependent pathway ([68](#), [69](#)). Induction of Type I interferon within the TME is required for generation of Type I interferon-dependent innate and adaptive antitumor immunity by potentiating the cross-priming capacity of tumor-infiltrating antigen-presenting cells, such as dendritic cells, as well as recruitment and effector function of CD8+ T effector cells ([70](#), [71](#)).

Exosomes are small (30–150 nm) vesicles containing unique RNA and protein cargo, secreted by all cell types in culture. They are also found in abundance in body fluids including blood, saliva, and urine ([72-74](#)). Interest towards exosomes, from their function in the body to more practical applications, such as the use in diagnostics (based on analysis of their miRNA and protein content) and therapeutics development, has grown exponentially in the last 5 years ([75](#)). With the current advances the analysis of exosomal miRNA from biological samples such as blood is more feasible than ever before. Furthermore, the cargo contained in exosomes provides an enriched population of miRNA free of endogenous RNA contaminants such as ribosomal RNA (rRNA). Therefore, these exosomes contains a disease-specific miRNA signature, which is very attractive for diagnostic purposes ([76-78](#)).

Investigators have also examined the interactions of cancer-derived exosomes with primary T-lymphocytes ([79-82](#)). For example, previous studies have demonstrated that these cancer-derived exosomes induce apoptosis in CD8+ T-lymphocytes through the FAS/FASL pathway. Other studies have demonstrated that tumor-derived exosomes up-regulate expression of inhibitory genes in conventional CD4+T cells and their conversion into CD4+ CD25high FOXP3+ CD39+ Treg ([83](#), [84](#)), which co-expressed IL-10 and TGF- $\beta$ , CTLA-4, granzyme B/perforin and effectively mediated immune suppression.

RT can also induce extensive immunogenic alterations of dying and surviving cancer cells within the tumor microenvironment. The resulting stress and death of tumor cells could stimulate tumor-specific immune responses through the liberation of 'danger' signals or damage-associated molecular patterns, together with tumor-associated

[figure not shown]

antigens. Specialized antigen-presenting cells can capture tumor antigens and concurrently activate the 'danger' signals by engaging their corresponding pattern recognition receptors, such as toll-like receptors on the surface of immune cells ([85](#), [86](#)). The resultant antigen presentation can potentially lead to recruitment and priming of T cells and consequent immune-mediated destruction of tumors and/or metastases ([87](#)).

### 1.9.2 Preliminary Studies

[figure not shown]
The VCU Department of Radiation Oncology has an ongoing blood draw study (HM-12181) collecting blood samples from patients receiving RT with curative intent for cancer of the thorax (lung, breast, prostate, rectal, cervical, head and neck). We have published a preliminary analysis of retrospective patient blood samples collected for single-nucleotide polymorphisms (SNPs) in genes encoding HO-1, eNOS, NRF2 and TGF- $\beta$ 1 ([87](#)). NRF2 is a transcription factor for HO-1 expression and NRF2 knock-out mice are sensitive to radiation-induced lung injury ([88](#)). We also analyzed position -509 in the promoter of TGF- $\beta$ 1 because the minor allele is associated with enhanced promoter activity and TGF- $\beta$ 1 expression and previous studies had generated conflicting results of whether the minor allele was predictive for the late effects of radiotherapy. This study showed that polymorphisms of 3 genes involved in wound repair and response to radiation potentially predicted late normal tissue toxicity if racial differences in polymorphism frequencies are considered. Increased frequency of a long GT repeat in the promoter was associated with late effects in both African-Americans and Caucasian patient populations. SNPs in the TGF $\beta$ 1 and NRF2 promoters were significantly associated with late effects in African-Americans but not Caucasians. These latter findings demonstrate that the demographics of the VCU patient population and tissue bank will allow us to test for racial differences in the response of tissues to radiation.

In a preliminary study (Serrano et al, in preparation), exosomes were isolated from the plasma of patients with lung cancer on HM12181 the day before RT started, 3 weeks into RT and 6 months after the end of treatment ([Figure 1](#)). Exosomes from patients with recurrence isolated 6 months post-RT recovered their growth-promoting property in contrast to exosomes from patients who demonstrated no tumor recurrence. These results suggest the potential for exosomal biomarkers of tumor recurrence after therapy.

**Figure 1.** Exosomes Isolated from the Plasma of Patients with Lung Cancer Stimulate Fibroblast Proliferation

The relative expression levels of 10 different miRs selected on the basis of their roles in lung cancer were also determined: let-7a-5p, miR-20a-5p, miR-21-5p, miR-30b-5p, miR-106a-5p, miR-146a-5p, miR-155-5p, miR-200b-5p, miR-203a, and miR-208a-5p. Expression of 6 miRs demonstrated significant difference between recurrent and non-recurrent groups of lung cancer patients ([Figure 2](#)). Results are shown as an average of miRs expression (Cq-values) for recurrent (3 patients) and non-recurrent (3 patients) lung cancer before, during, and 6 months after therapy. Given the exponential property of Cq, the differences observed between the recurrent and non-recurrent patients are orders of magnitude. The Cq-values were normalized with respect to plasma volume. If the Cq-values are converted into fold differences, there is a significant difference between miR expression before and after therapy in the non-recurrent group (eg, let-7a demonstrates >5-fold decrease, miR-21 demonstrates >10-fold decrease). miR-155 is most probably absent at all time points in the non-recurrent group. When plasma exosome concentration numbers are determined, patients in the non-recurrent group consistently demonstrated only 3- to 5-fold decrease of exosome concentrations suggesting that the tumor cell is not an exclusive source of these exosomes, at least at 6 months post-therapy.

**Figure 2.** miR Analysis of Plasma Exosomes from Patients with Lung Cancer Normalized to Plasma Volume Extracted

qRT-PCR analysis of miR expression in exosomes isolated from the same patients as those in [Figure 1](#). Exosomal miRs were purified with kits from Norgen and, as discussed in the text, 10 miRs were analyzed. Additionally, two RNA spike-in controls were used: UniSp6 as the cDNA synthesis control, and UniSp3 as the interplate calibrator. Cq – quantification cycle; UDT – Cq undetermined after 45 cycles.

### 1.9.3 Biological Objectives

We will conduct correlative immunologic endpoints within each patient pre- to post-therapy and across the cohort of patients to elucidate the mechanistic immunologic effects of therapy. Blood samples will be obtained from patients prior to initiating SRT, prior to the second fraction of SRT, at the end of SRT, and at 8, 24, and 52 weeks post-SRT.

De-identified blood samples will be processed to collect buffy coat. Immune monitoring of blood samples will be performed on samples collected from all patients longitudinally throughout the study. Analytical flow cytometry will be performed to enumerate the frequencies of immune cell populations, including CD8+ T cells, regulatory T cells (Treg, CD4+Foxp3+), and CD11b+CD14-CD33+ myeloid-derived suppressor cells (MDSCs). Immune cell functional status will be determined by combinational staining of markers for T-cell activation (perforin, granzyme B, CD69, and CD107) and exhaustion (PD-1, LAG-3, TIM-3, and CD244). DNA will be prepared from the buffy coat and subjected to qPCR evaluation of the expression of immune-related genes for example: T-cell activation-related cytokines (IFN- $\gamma$ ), immunosuppressive enzymes, and molecules (IDO, arginase, CTLA-4, PD-1/PD-L1).

Exosomes will be isolated from plasma using the Norgen kit ([Figure 1](#)) and quantified by acetylcholinesterase activity and protein. From 1.0 mL plasma we isolate between

0.7 and 3.0 mg exosomal protein and 6-12 ng exosomal miR depending on the patient and time point. Quality and quantity of miR are assessed using a bioanalyzer and an Agilent small RNA chip and kit. Protein and miR are sequentially isolated from exosomes using the Norgen kit. From our prior experience, for example in [Figure 1](#), we obtain sufficient amounts of exosomes from individuals to perform the proposed analyses, eg amount of exosomal miRs extracted from 0.7mL of serum is enough for at least 30,000 qPCR reactions. qRT-PCR is the gold standard for miR measurement.

For functional analysis of exosomes, we will determine whether exosomes isolated from cancer patients as described above induce apoptosis of activated CD8+ T cells isolated from anonymized blood samples purchased from a local blood bank ([79-82](#)). Additional experiments will test whether tumor-derived exosomes mediate immune suppression by stimulating proliferation of conventional CD4+ T cells and their conversion to CD4+CD25highFoxP3+CD39+ Treg cells expressing IL-10, TGFβ, CTLA-4, and granzymeB/perforin ([83, 84](#)). Experiments described above in [Figure 1](#) evaluating whether exosomes stimulate fibroblast proliferation will be continued.

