### **2.2 Secondary Objectives**

In patients who have received study treatment (SRT and PD-1/PD-L1 inhibitor):

- 2.2.1 To determine the response rate of SRT and PD-1/PD-L1 inhibiting therapy per unidimensional immune-related response criteria (irRC) and, if brain metastases are present, per iRANO
- 2.2.2 To determine the response rate at irradiated tumor sites
- 2.2.3 To determine the response rate at non-irradiated tumor sites
- 2.2.4 To determine the 2-year survival rate
- 2.2.5 To assess the toxicity associated with the study treatment
- 2.2.6 To assess the radiobiological and immunological characteristics of patients receiving study treatment using blood samples collected before and after SRT

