### 3.4 Secondary Endpoints

- 3.4.1 Proportion of patients alive and free from progression (ie, CR, PR, or SD) per unidimensional irRC and, if brain metastases are present, per iRANO criteria at 24 weeks following SRT
- 3.4.2 Proportion of patients with treatment response (ie, CR, PR, or SD) at irradiated tumor sites at 24 weeks following SRT (refer to Section [10.1](#) for response criteria)
- 3.4.3 Proportion of patients with treatment response (ie, CR, PR, or SD) at non-irradiated tumor sites at 24 weeks following SRT (refer to Section [10.1](#) for response criteria)
- 3.4.4 Proportion of patients who are alive at 2 years after completion of SRT
- 3.4.5 Adverse events including the following:
  - All SRT-related and immunotherapy-related  $\geq$  grade 3 adverse events per the most current National Cancer Institute (NCI) Common Terminology Criteria for Adverse Events Version 5.0 (CTCAE v5.0) occurring from initiation of SRT until 8 weeks after the last SRT fraction
  - All immunotherapy-related adverse events (AEs) occurring from 8 weeks post-SRT until 2 years post-SRT requiring discontinuation of PD-1 or PD-L1 inhibiting therapy and concurrent initiation of immunosuppressive agents such as steroids as described in Section [8.5.2](#).

- 3.4.6 Radiobiological signature as described in Section [1.9.3](#) using blood samples collected prior to SRT (baseline), prior to the 2nd SRT fraction, immediately following completion of SRT (on same day); and at 8, 24, and 52 weeks following completion of SRT

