# 11 CORRELATIVE STUDIES

Refer to Section [1.8](#) for a description of the plans for correlative studies using collected blood samples.

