#### **11.4 Instructions for Blood Sample Collection**

At each time point:

- Collect 10 mL of blood in a purple-top tube
- Invert 8-10 times after collection and deliver at ambient temperature within 2 hours following collection to the laboratory of [name] in the Department of Radiation Oncology.

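### Section 1.9.3 measures immune-gene expression by qPCR on buffy-coat DNA; as written, that preparation cannot show a change in expression (minor; the wording of 1.9.3 needs correcting)

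*Combined protocol and SAP*

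**What the plan says.** Secondary objective 2.2.6 is "To assess the radiobiological and immunological characteristics of patients receiving study treatment using blood samples collected before and after SRT". Its endpoint, 3.4.6, is the "Radiobiological signature as described in Section" 1.9.3, at six time points from baseline to 52 weeks after SRT. The endpoint therefore has no content of its own beyond what 1.9.3 describes.

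On processing, Section 1.9.3 says "De-identified blood samples will be processed to collect buffy coat". It plans flow cytometry for cell frequencies and functional markers, and then says "DNA will be prepared from the buffy coat and subjected to qPCR evaluation of the expression of immune-related genes". The genes are introduced as examples: IFN-gamma, IDO, arginase, CTLA-4 and PD-1/PD-L1. Exosomes are isolated from plasma, and for their miR content the section says "qRT-PCR is the gold standard for miR measurement".

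Section 11 covers collection, labelling and tracking. It names no assay and sends the reader to Section 1.8 "for a description of the plans for correlative studies using collected blood samples". Section 1.8 is about volumetric tumour measurement; the blood assays are in 1.9.

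**The concern.** The sentence names one material and a quantity that this material cannot supply. A cell carries the same copies of the IFN-gamma gene whether the gene is silent or active. qPCR on genomic DNA returns gene copy number, and that should be the same before SRT, after SRT and at 52 weeks. Expression has to be read from RNA, converted to cDNA.

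What is at stake is the within-patient change over time that 1.9.3 sets out to describe. Of the named genes, only PD-1 has another planned readout in patients' cells, as an exhaustion marker in the flow panel. CTLA-4 appears otherwise only in the exosome experiments on Treg conversion, which do not follow expression in patients' leukocytes over time. IFN-gamma, IDO, arginase and PD-L1 have no other planned patient readout. IFN-gamma matters most here, because Section 1.9.1 cites its dose-dependent rise with radiotherapy as part of the rationale.

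**Working it through.** The plan gives no figure to reproduce, and the point depends on no alpha, power or rate. The check is a reading of every place where the assay could be specified.

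1. **Material and quantity.** Section 1.9.3 gives DNA as the material, qPCR as the method and expression as the quantity. The first and third do not fit together.

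2. **Is the missing step stated elsewhere?** Sections 1.9.2, 1.9.3 and 11.1 to 11.7 contain no RNA extraction, cDNA synthesis or reverse transcription for the buffy coat. Section 11.4 says "Collect 10 mL of blood in a purple-top tube" and gives mixing and delivery instructions only. Section 11.6 says who does the testing, not how.

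3. **How does the plan treat the parallel RNA assay?** For exosomal miR, 1.9.3 names qRT-PCR and a small-RNA chip. The preliminary work in 1.9.2 used RNA spike-ins, with "UniSp6 as the cDNA synthesis control". The reverse-transcription step is thus explicit for miR and absent for the buffy coat.

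4. **Which parts of 3.4.6 depend on the DNA sentence?**

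| Component in 1.9.3 | Depends on the DNA preparation? |
|---|---|
| Flow cytometry (cell frequencies, activation, exhaustion) | No |
| Exosome quantification | No |
| Exosomal miR by qRT-PCR | No |
| Exosome functional assays | No |
| Immune-gene expression by qPCR | Yes |

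5. **How many samples?** Sampling is required of all patients (Section 11.1), and Section 13.2 allows up to 46 enrolled.
 - Ceiling: 6 time points × 46 patients = 276.
 - The 52-week draw depends on the patient being available and willing (Table 5, footnote O). Without it: 5 × 46 = 230.
 - Counting only the 42 efficacy-evaluable patients gives 6 × 42 = 252, which is not the ceiling because sampling is not limited to them.
 - If the trial closes after stage 1, the 14 evaluable patients give 6 × 14 = 84 planned draws.

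**The case against.** The strongest reply is that this is a wording slip. The stated target is expression, and the same group's preliminary miR work used reverse transcription with a cDNA control. The plan also uses qPCR loosely: 1.9.3 expresses its miR yield in qPCR reactions although reverse transcription is clearly intended there. On that reading, DNA stands for RNA or cDNA and the laboratory would do the right thing. The opposite slip is also possible. The group's earlier published blood work (1.9.2) was SNP genotyping, for which DNA is the correct material, so expression may be the wrong word. The documents do not settle which. This part of the objection stands, and it is why the fix offers both routes. It does not remove the point, because 1.9.3 is the only assay instruction behind a named secondary endpoint.

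A reader might also infer several stronger things that the documents do not support:

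- **That the readout cannot be obtained from the sample collected.** Buffy coat contains leukocyte RNA, so an aliquot of the same tube can supply it.
- **That the RNA would be lost for good.** No section says that only DNA is kept or that remaining buffy coat is discarded; storage and disposal are not addressed.
- **That the tube and ambient delivery in Section 11.4 are a separate defect.** That section instructs those who draw and deliver the blood. Its silence on RNA stabilisation does not show that the laboratory has no such step.
- **That a fixed gene panel is lost.** The genes are only examples.
- **That a flat result would pass as absence of immune activation.** This is speculative, since flow cytometry measures activation and exhaustion separately.

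**Conclusion.** The point holds in a limited form and is minor. The preparation in 1.9.3, followed literally, cannot yield the expression readout that the same sentence promises, and no other section corrects it. One component of correlative endpoint 3.4.6 is affected, at no more than 276 samples and probably fewer.

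The primary endpoint, sample size, error rates and safety analyses do not depend on it. Section 13.4 specifies no test on this endpoint.

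The conclusion rests on reading DNA as genomic DNA. If RNA or cDNA was meant, only the text is at fault, and it still needs correcting. If a DNA-based quantity was meant, the word expression is the error.

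**What to change.** In Section 1.9.3, choose one of two wordings.

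- **If expression is intended:** state that RNA is extracted from a buffy-coat aliquot of the same tube and reverse-transcribed before qPCR, with results normalised to reference genes. State the matching laboratory handling on receipt, in Section 11 or in a laboratory procedure to which it refers.
- **If DNA is intended:** replace expression with the DNA-based quantity to be measured, and say what a change from before to after SRT would mean for it.

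In either case, correct the pointer at the head of Section 11 from 1.8 to 1.9.

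The cost is a few lines of text and, on the first route, a different extraction kit plus a reverse-transcription step for an aliquot of blood already drawn. No extra blood or visit is needed. If samples have already been processed, the laboratory should confirm which nucleic acid was prepared and whether any buffy coat remains.
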